11.9 Safety Analyses

The safety analyses will be performed for the Safety population. The primary safety endpoint will be the proportion of participants who experience one or more device-related AEs for each application and overall. The proportion and exact 95% confidence interval will be computed. Any changes in corrected distance visual acuity or slit lamp biomicroscopy findings will be summarized.

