9.2 Adverse Event Evaluation

The Investigator should evaluate if each AE is serious, related to the investigational device and anticipated using the following definitions.

A serious adverse event (SAE) is defined as any untoward medical occurrence that:

- It results in death (i.e., the AE actually causes or leads to death);
- It is life threatening (i.e., the AE places the participant at immediate risk of death);
- It requires or prolongs inpatient hospitalization. If a participant is hospitalized to undergo a medical or surgical procedure as a result of an AE, the event responsible for the procedure, not the procedure itself, should be recorded as the event. For example, if a participant is hospitalized to undergo coronary bypass surgery, the heart condition that necessitated the bypass should be recorded. Hospitalizations for diagnostic or elective surgical procedures or

hospitalizations required to allow outcome measurement for the study should not be recorded as SAEs:

- It results in persistent or significant disability/incapacity (i.e., the AE results in substantial disruption of the participant's ability to conduct normal life functions);
- It results in a congenital anomaly/birth defect in a neonate/infant born to a mother exposed to the investigational device;
- It is considered a significant medical event by the investigator based on medical judgment (e.g. may jeopardize the participant or may require medical/surgical intervention to prevent one of the outcomes listed above);
- It is considered sight-threatening by the Investigator.

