9.3 Relationship of the AE to the investigational device

Definite	A clear cut causal relationship with the study device and no other possible cause
Probable	A causal relationship with the study device is likely although alternate etiologies are also possible
Possible	A causal relationship with study device is not definite, alternate etiologies are also possible
Not related	The AE has no causal relationship to study device and/or there is evidence of alternative etiology such as concurrent medication or illness.
Not applicable	The participant has not been exposed to the study device.

The AE will be determined to be device-related, making it an adverse device effect (ADE), if it is identified to have had a definite, probable or possible causal relationship to the investigational device.

An AE is unanticipated if the nature, severity, or frequency of the event is not consistent with either the known or foreseeable risk of AEs associated with the procedures involved in the research that are described in (a) the protocol-related documents, such as the IRB-approved research protocol, user manuals and the current IRB-approved informed consent document, and (b) other relevant sources of information such as product labeling and package inserts; or the expected natural progression of any underlying disease, disorder, or condition of the participant(s) experiencing the AE and the participant's predisposing risk factor profile for the AE.

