9.5 Adverse Event Reporting

All AEs that occur during the course of the study should be reported on the Adverse Event CRF. The Investigator should determine the intensity of the event.

Mild	Awareness of sign or symptom, but easily tolerated
Moderate	Discomfort enough to cause interference with normal daily activities
Severe	Inability to perform normal daily activities

All SAEs and ADEs should be reported by the Investigator to [REDACTED] and the Sponsor in writing within 24 hours from the point in time when the Investigator becomes aware of the event. It is the responsibility of the Investigator to promptly notify the Institutional Review Board (IRB) of all unanticipated SAEs and unanticipated problems, per the IRBs reporting requirements.

Throughout the course of the proposed study, all efforts will be made to remain alert to possible adverse experiences or untoward findings. If adverse experiences occur, the first concern will be the safety and welfare of the participant. Appropriate medical intervention will be made.

[REDACTED] and the Sponsor will immediately conduct an evaluation of any UADE. The results of the evaluation will be reported to the IRB within 10 days of [REDACTED] and/or the Sponsor becoming aware of the event. If it is determined by [REDACTED] and the Sponsor to present an unreasonable risk to study participants, all investigations or parts of the investigation presenting that risk will be terminated as soon as possible. Termination will occur not later than five working days after [REDACTED] and the Sponsor makes this determination, and not later than 15 working days after first receiving notice of the event. [REDACTED] and the Sponsor will not resume an investigation terminated under these conditions without an additional IRB approval.

Contact information for reporting Serious Adverse Events:

[REDACTED]	[REDACTED]
------------	------------

Sponsor Contact Information	
[REDACTED]	[REDACTED]

Office [contact]
-------------------	--------------

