9.6 Anticipated Adverse Events

The following is a list of potential AEs associated with the use of the device:

- Nasal discomfort or pain
- Epistaxis
- Excessive sneezing
- Nasal irritation, paresthesia or numbness post-stimulation
- Nasal infection, abrasion or inflammation
- Skin irritation or hypersensitivity
- Headache (e.g., tension, migraine, etc.)
- Facial pain
- Excessive salivation
- Sensation of teeth vibrating
- Excessive rhinorrhea
- Temporary aggravation of nasal allergies
- Allergic reaction to contact materials

The following is a list of potential AEs associated with the testing procedures at Screening or with CAE exposure:

- Ocular discomfort
- Moderate or severe conjunctival injection
- Clinically significant decrease in visual acuity
- Clinically significant increase in corneal or conjunctival epithelial defects
- With use of proparacaine, temporary burning, stinging and conjunctival redness of the eyes
- With use of proparacaine, a rare hyperallergic corneal reaction characterized by epithelial keratitis, sloughing of epithelium, corneal filaments and iritis
- With the Schirmer test, corneal irritation and abrasion
- Allergic reaction to contact materials

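### Section 11.9 as visible analyses only device-related AEs, so events due solely to the CAE or a study test, and SAEs rated unrelated, enter no specified AE summary

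*Combined protocol and SAP*

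**What the plan says.** **Collection.** Section 9.5 is inclusive: "All AEs that occur during the course of the study should be reported on the Adverse Event CRF". It also requires every SAE, whatever its cause, to reach the sponsor within 24 hours. Section 9.0 starts AE capture when the participant enters the CAE.

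**Rating.** Section 9.2 sets out what is judged: "The Investigator should evaluate if each AE is serious, related to the investigational device and anticipated using the following definitions". Section 9.5 adds intensity. Under section 9.3 an AE counts as device-related "if it is identified to have had a definite, probable or possible causal relationship to the investigational device". The remaining ratings are 'Not related' and, for participants not yet exposed to the device, 'Not applicable'.

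**Known sources of harm.** Section 9.6 has two lists. One covers the device. The other is introduced by "The following is a list of potential AEs associated with the testing procedures at Screening or with CAE exposure" and has eight entries.

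**Analysis.** Section 11.9 states: "The primary safety endpoint will be the proportion of participants who experience one or more device-related AEs", both per application and overall. It continues: "The proportion and exact 95% confidence interval will be computed". The only other safety output is this: "Any changes in corrected distance visual acuity or slit lamp biomicroscopy findings will be summarized". The analysis uses the Safety population, which section 11.4 equates with the FAS, meaning participants who initiated at least one device application.

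**The concern.** The protocol recognises two sources of harm, the device and the study's own challenge and tests, but rates causality for one and analyses AEs for one. CAE exposure is deliberate: about 120 minutes on Day 0 (section 8.4.2), with a second CAE visit on Day 45.

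The study has a single arm and is open-label (section 4.0), so there is no control rate against which to read the device-related proportion, and the investigator attributing cause is unmasked. An all-cause proportion is the usual companion figure because it does not depend on that attribution. Without it, a reader cannot tell whether a low device-related rate reflects few events or many events attributed elsewhere. Harm from the CAE and the tests is not estimated at all.

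**Working it through.** The plan gives no AE rate and no safety precision target, so there is no figure of its own to reproduce. The check is to follow each kind of event from collection to analysis.

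| Event | Captured? | Rating under 9.3 | In the 11.9 AE proportion? |
|---|---|---|---|
| Due to the device, or cause not separable from it | Yes | Definite, probable or possible | Yes |
| Due solely to the CAE or a later study test, after device exposure | Yes | Not related | No |
| Due to the CAE, before the first application on Day 0 | Yes | Not applicable | No |
| SAE judged unrelated to the device | Yes, and reported within 24 hours | Not related | No |
| Due to a Screening test | No; precedes CAE entry | None | No |

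**What the other outputs recover.** Acuity and slit lamp summaries bear on three of the eight entries in the second 9.6 list: acuity loss, conjunctival injection and epithelial defects. They do so as examination findings, without AE incidence, intensity or cause. Section 11.6 tabulates withdrawals with reasons, which shows only those AEs that end participation.

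**What the CRF could recover later.** All-cause counts could be produced from the AE CRF. Procedure causality could not be recovered cleanly, because 'Not related' pools CAE and test effects with concurrent illness and medication. The anticipated/unanticipated rating refers to research procedures but does not record cause.

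**Denominator.** Section 11.1 reports that about 10% of participants in an earlier study did not reach the application threshold in the CAE. Assume the same rate on Day 0, and that those participants never apply the device: 0.10 × 60 = 6 would have been exposed to the CAE but be outside the Safety population, leaving 60 − 6 = 54. The number is smaller if some of them apply the device at another time. An all-cause table restricted to the Safety population would therefore still miss part of the group exposed to the challenge.

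**Precision of the added rows.** This is illustration only; the counts are assumed. The exact (Clopper-Pearson) limits for x events in n participants are the 0.025 quantile of Beta(x, n − x + 1) and the 0.975 quantile of Beta(x + 1, n − x). With n = 60:

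| Participants with event | Proportion | Exact 95% CI |
|---|---|---|
| 0 | 0% | 0 to 6.0% |
| 3 | 5% | 1.0% to 13.9% |
| 6 | 10% | 3.8% to 20.5% |
| 12 | 20% | 10.8% to 32.3% |

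The intervals are wide but informative. For example, no SAE among 60 participants would still be compatible with a rate up to 6.0%.

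**The case against.** The strongest reply has four parts.

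1. **The device-related definition is broad.** A 'possible' relationship allows for other causes and still counts. The device is applied inside the CAE and during the Visit 3 Schirmer test, so an event that cannot be separated from the device enters the endpoint. This stands, and it limits the gap to events rated 'Not related' or 'Not applicable'.
2. **Coverage is partial, not absent.** Acuity and slit lamp changes are summarised whatever their cause, withdrawal reasons are tabulated, and SAEs are reported promptly. This also stands, but none of these is an AE or SAE incidence.
3. **Redaction.** The synopsis blocks on safety measures and safety analyses, and section 6.2, are blacked out. Section 11.9 names a primary safety endpoint without saying it is the only AE summary. A reader might infer that the plan contains no all-cause analysis anywhere; the documents do not allow that. They support the narrower statement that 11.9, the governing analysis section and readable in full, does not specify one.
4. **The CAE is a challenge model and the study is about the device.** That justifies the choice of primary safety endpoint. It does not explain why harms the protocol lists are left without a summary.

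Two further inferences are tempting and wrong. A reader might say that a CAE-caused event has no causality category. It has one, 'Not related' or 'Not applicable'; what is missing is a code separating it from other non-device causes. A reader might also assume that all harms on the second 9.6 list are at least collected. Those of the Screening tests are not, because capture begins at CAE entry.

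**Conclusion.** The concern holds in limited form. On the visible text, section 11.9 specifies one AE analysis and no summary of all AEs or all SAEs. AEs from CAE entry onward that are due solely to the CAE or a study test, and SAEs rated unrelated, fall outside it. The only AE estimate therefore depends on unmasked attribution in a study with no control arm.

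The size of the omission cannot be derived, since the documents give no AE rates. Any contrast between a device-related and an all-cause percentage would come entirely from assumed counts and would not be evidence of impact.

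The conclusion assumes that the redacted blocks contain no all-cause summary. The estimate of about 6 CAE-exposed participants outside the Safety population assumes that the earlier study's threshold rate carries over and that those participants never use the device. No effectiveness result, hypothesis or sample size is affected. The change should be made because procedure causality that is not recorded prospectively is hard to reconstruct.

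**What to change.** - Keep the device-related proportion as the primary safety endpoint.
- Add to section 11.9 the number and proportion, with exact 95% CI, of participants with any AE and with any SAE, regardless of causality. Use all participants who entered the CAE as the denominator, so that those who never applied the device are included.
- Add one item to the AE CRF for relationship to CAE exposure or a study procedure, on the scale of section 9.3, and report that proportion in the same way.
- Reconcile section 9.0, under which Screening-test harms are not captured, with section 9.6, which lists them as potential AEs. The new CRF item alone would not recover them.
- If the redacted sections already provide an all-cause summary, refer to it in 11.9 and state its denominator.

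Cost: one table and one CRF item, with no new visit or assessment. The downside is that a larger all-cause figure may stand beside the headline rate.

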12.0 FINAL CLINICAL STUDY REPORT

A final clinical study report will be prepared after completion of the study.

13.0 COMPLIANCE WITH GOOD CLINICAL PRACTICES, ETHICAL CONSIDERATIONS, AND ADMINISTRATIVE ISSUES

13.1 Protection of Human Participants

13.1.1 Participant Informed Consent

Informed consent should take place before any study-specific procedures are initiated. Signed and dated written informed consent should be obtained from each participant and/or from the participant's parent or legal guardian prior to enrollment into the study.

All ICFs should be approved for use by the Sponsor and receive approval/favorable opinion from an IRB prior to use. If the consent form requires revision (e.g., due to a protocol amendment or significant new safety information), it is the Investigator's responsibility to ensure that the amended informed consent is reviewed and approved by Sponsor and [REDACTED] prior to submission to

the governing IRB and that it is read, signed and dated by all participants subsequently enrolled in the study as well as those currently enrolled in the study if required by the governing IRB.

If informed consent is taken under special circumstances (oral informed consent), then the procedures to be followed should be determined by [REDACTED] and/or study Sponsor and provided in writing by [REDACTED] and/or study Sponsor prior to the consent process.

13.1.2 Institutional Review Board (IRB) Approval

This study is to be conducted in accordance with IRB regulations (U.S. 21 Code of Federal Regulations [CFR] Part 56.103). The Investigator should obtain appropriate IRB approval before initiating the study and re-approval at least annually.

13.1.3 Ethical Conduct of the Study

This study will be conducted in compliance with the protocol, Good Clinical Practices (GCPs), including the International Conference on Harmonisation (ICH) Guidelines, and the ethical principles that originated with the Declaration of Helsinki.

13.1.4 Participant Confidentiality

All personal study participant data collected and processed for the purposes of this study should be maintained by the Investigator and his/her staff with adequate precautions to ensure that the confidentiality of the data is in accordance with local, state, and federal laws and regulations.

Monitors, auditors and other authorized representatives of [REDACTED] the Sponsor, the IRB approving this study, the Food and Drug Administration (FDA), the Department of Health and Human Services (DHHS), and other domestic government agencies, will be granted direct access to the study participant's original medical and study records for verification of the data and/or clinical trial procedures. Access to this information will be permitted to the aforementioned individuals to the extent permitted by law.

A report of the results of this study may be published or sent to the appropriate health authorities in any country in which the study device may ultimately be marketed, but the participant's identity will not be disclosed in these documents.

13.2 Documentation

Source documents may include a participant's medical records, hospital charts, clinic charts, the Investigator's study participant files, as well as the results of diagnostic tests such as X-rays, laboratory tests, and electrocardiographs. The Investigator's copy of the CRFs serves as the Investigator's record of a participant's study-related data.

13.2.1 Retention of Documentation

All study-related correspondence, participant records, consent forms, record of the distribution and use of all study device and copies of CRFs should be maintained on file for at least two years after the last approval of a marketing application in an ICH region and until there are no pending or contemplated marketing applications in an ICH region; or until

at least two years have elapsed since the formal discontinuation of clinical development of the study device. These documents will be retained for a longer period if required by the applicable regulatory requirements or by an agreement with the Sponsor. It is the responsibility of the Sponsor to inform the Investigator/institution as to when these documents no longer need to be retained.

If the responsible Investigator retires, relocates, or for other reasons withdraws from the responsibility of keeping study records, custody should be transferred to a person who will accept the responsibility. The Sponsor should be notified in writing of the name and address of the new custodian.

13.3 Regulatory Status

A previous version of the TrueTear (formerly known as the Oculeve Intranasal Lacrimal Neurostimulator) received CE Mark on December 22, 2014 (CE 615662). It has been approved for marketing in Canada and Australia as well. It is an investigational device in the US.

13.4 Labeling, Packaging, Storage, Accountability, and Return or Disposal of Study Device

All investigational devices will be clearly labeled “For Investigational Use Only.” A device accountability log recording the distribution and return of all devices will be maintained by the site and will be filed in the Trial Master File. Used disposable tips should be discarded after use; unused disposable tips should be returned to the Sponsor at the conclusion of the study.

13.5 Recording of Data on Source Documents and Case Report Forms (CRFs)

All participant data will be captured in the participant CRFs (i.e. source document). The Investigator is responsible for ensuring that study data is completely and accurately recorded on each participant’s CRF and all study-related materials. All study data should also be attributable, legible, contemporaneous, and original. Recorded datum should only be corrected in a manner that does not obliterate, destroy, or render illegible the previous entry (e.g., by drawing a single line through the incorrect entry and writing the revision next to the corrected data). An individual who has corrected a data entry should make clear who made the correction and when, by adding to the correction his/her initials as well as the date of the correction.

13.6 Amendments to the Protocol

Any amendment containing major modifications (particularly if it may involve an increased risk to the participants) should be approved by the IRB before it may be implemented. No change in the conduct of the study can be instituted without written approval from the Sponsor.

13.7 Publications

Information collected during this clinical study concerning TrueTear and results of the data obtained are proprietary and strictly confidential. The Sponsor reserves all rights to any such information. Authorship and manuscript composition will reflect cooperation among all parties

involved in the study. Authorship will be established before writing the manuscript. Sponsor and [REDACTED] will have the final decision regarding the manuscript and publication.

[figure not shown]

15.0 APPENDICES

15.2 Appendix 2: Examination Procedures, Tests, Equipment, and Techniques

15.2.1 Visual Acuity Procedures

LogMAR visual acuity should be assessed using an ETDRS chart. The procedure used will be consistent with the recommendations provided for using the ETDRS eye chart. Visual acuity should be evaluated at the beginning of each visit in the study (i.e., prior to slit lamp examination). Participants should use the most recent correction to attain their corrected distance visual acuity (CDVA); if they forget their spectacles, this prescription can be placed in a trial frame.

Equipment

The visual acuity chart to be used is the ETDRS chart. If smaller reproduction (18" by 18", e.g., from Prevent Blindness) wall charts are used, the participant viewing distance should be exactly 10 feet (or as specified by the manufacturer). In ALL cases, for purposes of standardizing the testing conditions during the study, all sites should use only ETDRS Series 2000 Chart 1 & 2, and the right eye should be tested first. For reflectance (wall) charts, the chart should be placed frontally and be well illuminated.

Measurement Technique

The chart should be at a comfortable viewing angle. The right eye should be tested first. The participant should attempt to read each letter, line-by-line, left to right, beginning with line 1 at the top of the chart. The participant should be told that the chart has letters only, no numbers. If the participant reads a number, s/he should be reminded that the chart contains no numbers, and the examiner should then request a letter in lieu of the number. The participant should be asked to read slowly, so as to achieve the best identification of each letter. S/he is not to proceed to the next letter until s/he has given a definite response.

If the participant changes a response (e.g., 'that was a "C" not an "O"') before s/he has read aloud the next letter, then the change should be accepted. If the participant changes a response having read the next letter, then the change is not accepted. The examiner should never point to the chart or to specific letters on the chart during the test.

A maximum effort should be made to identify each letter on the chart. When the participant says s/he cannot read a letter, s/he should be encouraged to guess. If the participant identifies a letter as one of two letters, s/he should be asked to choose one letter and, if necessary, to guess. When it becomes evident that no further meaningful readings can be made, despite encouragement to read or guess, the examiner should stop the test for that eye. However, all letters on the last line should be attempted as letter difficulties vary and the last may be the only one read correctly. The number of letters missed or read incorrectly should be noted.

LogMAR Visual Acuity Calculations

The last line in which a letter is read correctly will be taken as the base logMAR reading. To this value will be added the number " $N \times 0.02$ " where 'N' represents the total number of letters

missed up to and including the last line read. This total sum represents the logMAR visual acuity for that eye.

Example: Participant correctly reads 4 of 5 letters on the 0.2 line, and 2 of 5 letters on the 0.1 line.

Base logMAR	= 0.1
N (total number of letters incorrect on line 0.2 as well as 0.1)	= 4
$N \times T$ ($T=0.02$)	= 0.08
Base logMAR + ($N \times T$)	= 0.1 + 0.08
logMAR visual acuity	= 0.18

Repeat the procedure for the left eye.

In order to provide standardized and well-controlled assessments of visual acuity during the study, all visual acuity assessments at a single site should be consistently done using the same lighting conditions and same correction if possible during the entire study. If the same correction cannot be used (i.e., a participant broke his/her glasses), the reason for the change in correction should be documented.

Note: A clinically significant visual acuity decrease (defined as an increase of 0.22 or greater in logMAR score) from the Screening Visit (Visit 1) should be evaluated by the Investigator as a potential AE.

